#### **Perceived Stress Scale (PSS-14)**

Developed by Cohen et al. (1983), this scale assesses perceived stress over the past month. The Turkish adaptation was done by Eskin et al. (2013). It includes 14 items rated on a 5-point Likert scale. Higher scores indicate higher levels of perceived stress. In the current study, Cronbach's alpha was 0.91.

# Parents' Internalized Stigma of Mental Illness Scale (PISMI)

Developed by Boyd-Ritsher et al. (2003) and adapted to Turkish by Gül-Dikeç et al. (2019), this 29-item scale evaluates internalized stigma in parents of individuals with mental illness. It includes five subscales and uses a 4-point Likert scale. In this study, Cronbach's alpha was 0.96.

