# The Effect of a Video-Based Orientation Intervention and Feature Importance Analysis Using Support Vector Regression

### Method

## **Study Design**

This study was designed as a randomized controlled experimental study to evaluate the effect of a video-based orientation training on stress and stigma levels among caregivers of psychiatric patients. Participants were randomly assigned to either the intervention group (receiving video training) or the control group (receiving routine care).

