## **Research Questions and Hypotheses**

This study aimed to address the following research questions:

- Is video-based orientation training effective in reducing perceived stress levels among caregivers of psychiatric patients?
- Is the intervention effective in reducing stigmatizing attitudes and beliefs toward psychiatric disorders?
- What are the most important variables that determine perceived stress and stigma levels?

Accordingly, the following hypotheses were tested:

- H1: Video-supported orientation training reduces the perceived stress level of caregivers of psychiatric patients.
- H2: Video-supported orientation training reduces stigmatizing attitudes and beliefs toward psychiatric disorders.
- H3: Perceived stress and stigma levels are influenced by various factors such as the caregiver's demographic characteristics, psychiatric diagnoses, and the caregiving relationship.

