## **Place and Time of the Study**

The study will be conducted between July 15 and September 30, 2025, in the closed psychiatric ward of a university hospital located in northeastern Türkiye. The psychiatric unit is a mixed-gender service with a capacity of 16 beds, structured to provide evaluation, treatment, and follow-up for patients with severe psychiatric symptoms. The unit is designed to support both acute intervention and stabilization, ensuring adequate safety and observation. It also organizes educational and social activities to enhance patients' insight, social skills, and adaptation to society. Psychosocial skills training is primarily provided by nurses in collaboration with occupational therapists.

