## **Study Population and Sample**

The study population consisted of relatives of patients admitted to the psychiatric unit between July and September 2023 (n=60). Sample size was determined using power analysis with the G\*Power 3.1.9.7 software. Based on the perceived stress scale (PSS) mean scores reported in Zimmerman et al. (2023), the sample was calculated with a 5% type I error, 95% power, and an effect size of 0.924. Statistical analysis indicated that the study should include at least 56 participants (28 in each group). To account for potential data loss, 10% more participants were recruited, resulting in a total of 60 participants (30 in each group). Inclusion criteria: first-degree relatives (parent, spouse, or child) of admitted patients, aged 18 or older, willing to participate, and having sufficient reading, writing, and verbal communication skills. Exclusion criteria included individuals with a psychiatric diagnosis, history of alcohol or substance use, dementia, or other organic mental disorders based on DSM-5.

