#### **Data Collection Tools**

Data were collected through face-to-face interviews using a researcher-developed questionnaire, the Perceived Stress Scale-14 (PSS-14), and the Parents' Internalized Stigma of Mental Illness Scale (PISMI).

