#### **Procedure**

This randomized controlled trial was conducted in accordance with the CONSORT guidelines. The PSS-14 and PISMI were administered before (pre-test) and one week after (post-test) the video-based orientation intervention. The intervention included four 45–60-minute video-supported sessions conducted in a suitable meeting room. Training was provided by a psychiatric nurse in collaboration with a psychiatric nursing associate professor. Control group participants received traditional verbal orientation.

Session Content:

- 1. Introduction to the research and psychiatric unit via video and Q&A.
- 2. Explanation and discussion of stigma and personal caregiver experiences.
- 3. Basic knowledge about psychiatric disorders, treatment, and caregiving.
- 4. Understanding and coping with stigma, including influencing factors and family impact.

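### The H2 conclusion is wider than the stigma scale behind it: the PISMI is described as measuring internalized stigma in parents, while H2 concerns attitudes toward disorders in parents, spouses and children

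*Protocol*

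**What the plan says.** Four parts of the protocol bear on the stigma outcome.

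- **Instrument.** The section on the PISMI states that "this 29-item scale evaluates internalized stigma in parents of individuals with mental illness". It mentions five subscales without describing them, and reports a Cronbach's alpha of 0.96 in this study.
- **Respondents.** Study Population and Sample admits "first-degree relatives (parent, spouse, or child) of admitted patients".
- **Administration.** Procedure states that "The PSS-14 and PISMI were administered before (pre-test) and one week after (post-test) the video-based orientation intervention". It does not confine the PISMI to parents.
- **Claim.** Research Questions and Hypotheses gives "H2: Video-supported orientation training reduces stigmatizing attitudes and beliefs toward psychiatric disorders". The second research question asks: "Is the intervention effective in reducing stigmatizing attitudes and beliefs toward psychiatric disorders". Study Design uses a third, looser term: "stress and stigma levels among caregivers of psychiatric patients".

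Data Collection Tools lists three tools: a questionnaire developed by the researchers, whose content is not stated, the PSS-14 and the PISMI. The PSS-14 is described as measuring perceived stress. The PISMI is therefore the only one described as measuring stigma. That it serves H2 is an inference, but no other described tool could.

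**The concern.** The hypothesis, the eligible population and the instrument should describe the same quantity in the same people. Here they differ in two ways.

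1. **Who answers.** The scale is presented as one for parents, but spouses and adult children may enrol and are asked to complete it.
2. **What is measured.** H2 is worded as a change in views about psychiatric disorders. The scale is described as capturing stigma that the parent has internalized. In the protocol's own wording, the first is directed at disorders and the second is held by the respondent.

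At stake is the meaning and reach of the stigma result. A difference in PISMI scores, analysed exactly as planned, would be reported as a change in attitudes toward psychiatric disorders in all three kinds of relative. The described measure would support a statement about internalized stigma, and on the protocol's own description only in parents.

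**Working it through.** **Step 1: set the passages side by side.**

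| Element | PISMI section | Elsewhere in the protocol |
|---|---|---|
| Respondents | Parents | Parents, spouses and children (Study Population and Sample); no restriction when administered (Procedure) |
| Construct | Internalized stigma | Stigmatizing attitudes and beliefs about disorders (H2, second research question); stigma levels (Study Design) |
| Evidence of fit | Alpha 0.96 | No version for, or validation in, spouses or children is mentioned |

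The respondent mismatch is explicit. The construct mismatch is one of wording. Because the subscales are not described, the protocol neither shows that the PISMI covers what H2 names nor shows that it does not. Alpha reflects internal consistency. It does not establish validity in a particular kind of relative, or that the score is the construct in H2.

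**Step 2: can the effect on H2 be sized?** No. That would need the number of non-parents, the scale's performance in them and a stigma effect size, and the protocol gives none of these. Its one planning effect size, 0.924 with 28 per group, comes from PSS means and says nothing about the PISMI. There is no planning figure for stigma to reproduce.

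**Step 3: what would a parents-only analysis deliver?** This describes the cost of part of the remedy, not the size of the defect.

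Inputs: 30 per arm (Study Population and Sample; Randomization). The numbers of parents per arm are assumptions. The comparison is taken as an unadjusted difference of two means with a common SD.

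Formula, in SD units: half-width = t(0.975, n1 + n2 − 2) × √(1/n1 + 1/n2).

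| Parents per arm | Calculation | 95% CI half-width |
|---|---|---|
| 10 and 10 (assumed) | 2.101 × 0.447 | 0.94 SD |
| 15 and 15 (assumed) | 2.048 × 0.365 | 0.75 SD |
| 20 and 20 (assumed) | 2.024 × 0.316 | 0.64 SD |
| 15 and 5 (assumed) | 2.1009 × 0.5164 = 1.085 | 1.08 SD |
| 30 and 30 (all participants) | 2.002 × 0.258 | 0.52 SD |

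The uneven row is included because the Randomization section describes no stratification by relationship, so parents may split unevenly. The same 20 parents give 0.94 SD if split evenly and 1.08 SD if split 15 and 5.

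**The case against.** The strongest reply is that this is loose wording in a short protocol. It uses stigma as a general term in several places, the subscales are not described, and the cited development and adaptation papers may well support the scale in other relatives. A protocol need not reproduce validation evidence. Much of this stands. A reader might infer that the PISMI is invalid in spouses and children, or that it leaves out the attitudes H2 names. The document supports neither inference. What remains is that the protocol itself describes a parents' scale, gives it to non-parents without a stated justification, and words its hypothesis differently from its measure.

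A second reply is that both arms complete the same scale, so randomisation protects the comparison and poor fit would only dilute it. Randomisation does remove systematic bias between arms in expectation. It does not settle what the score means or whom the conclusion covers. Nor does the protocol support a claim of dilution only. In a trial of 60 with no described stratification, a chance imbalance in relationship could shift a post-test contrast either way if the scale behaves differently in non-parents. Equally, nothing shows that the contrast is biased.

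A third reply is that a parents-only analysis is analysis-plan detail. That is fair, and the analysis can be placed there. Eligibility, the hypotheses and the choice of instrument are protocol content, and it is these that disagree.

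A reader might also infer that the support vector regression for PISMI scores is compromised because H3 names the caregiving relationship. The regression section lists no features, so that is conditional and forms no part of this point.

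**Conclusion.** The point holds as an inconsistency in the current text. As written, H2 and the second research question go beyond the described measure in construct and in respondents. The respondent part is firm. The construct part rests on the protocol's wording alone.

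The size of any effect on the stigma result is unknown, and no figure is offered for it. The half-widths above should not be read as evidence of harm: they describe only the precision of an added analysis under assumed numbers of parents. A failure of measurement has not been shown. H1, which rests on the PSS-14, and the sample size, which rests on PSS means, are unaffected.

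The sponsor should correct this, because it changes what the trial may conclude about one of its three hypotheses. Confidence is medium, since that the PISMI serves H2 is inferred and the evidence behind the scale is not in the document.

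**What to change.** 1. Restate H2 and the second research question as internalized stigma measured by the PISMI. Keeping the present wording and narrowing only the conclusion would leave the mismatch in place.
2. Date that change and disclose whether scale data existed when it was made. The protocol states "The study will be conducted between July 15 and September 30, 2025", yet already reports an alpha from this study, so its text does not settle the question.
3. Keep the PISMI comparison in all relatives. Limit the validity claim to parents unless evidence for the scale in spouses and children is cited.
4. Add a PISMI analysis in parents only, labelled as sensitivity.

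**Cost.** Wording, a dated disclosure and one extra analysis. Eligibility, assignment, instrument and data collection do not change, and the relationship should already be known because it is an inclusion criterion. The downsides are a narrower H2 claim and an extra analysis too imprecise to settle the matter alone. With 10 parents per arm its half-width of 0.94 SD would exceed even the 0.924 planning effect, which is a PSS figure used here only for scale.

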#### **Procedure**

This randomized controlled trial was conducted in accordance with the CONSORT guidelines. The PSS-14 and PISMI were administered before (pre-test) and one week after (post-test) the video-based orientation intervention. The intervention included four 45–60-minute video-supported sessions conducted in a suitable meeting room. Training was provided by a psychiatric nurse in collaboration with a psychiatric nursing associate professor. Control group participants received traditional verbal orientation.

Session Content:

- 1. Introduction to the research and psychiatric unit via video and Q&A.
- 2. Explanation and discussion of stigma and personal caregiver experiences.
- 3. Basic knowledge about psychiatric disorders, treatment, and caregiving.
- 4. Understanding and coping with stigma, including influencing factors and family impact.

## **Statistical Analysis**

Statistical analyses were performed using R version 4.5.0. Descriptive statistics were computed, and appropriate tests (t-tests, Mann-Whitney U, Wilcoxon signed-rank, Chisquare, Fisher's exact, Pearson correlation) were applied based on data characteristics. Relationships were visualized with heat maps.

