#### Randomization

A total of 60 caregivers were randomly assigned to either the intervention or control group (30 each). Group assignment was carried out using the envelope method to prevent bias. Each envelope contained a note stating either "Intervention Group" or "Control Group" and was randomly selected by the participants themselves.

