## **Support Vector Regression-Based Feature Importance Analysis**

Support Vector Regression (SVR) was used to identify clinical and sociodemographic predictors of PSS and PISMI scores. SVR is suitable for small, nonlinear, and high-dimensional datasets common in psychiatry. Feature importance was evaluated using permutation-based analysis, with RMSE increases indicating variable contribution.

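### Both scales are measured before and after the intervention, but no listed arm comparison adjusts for the pre-test score, so available precision is lost

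*Protocol*

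**What the plan says.** The Procedure section collects both outcomes twice: "The PSS-14 and PISMI were administered before (pre-test) and one week after (post-test) the video-based orientation intervention". Each participant therefore has a pre-test value on the scale used to judge the effect.

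The Statistical Analysis section names its methods: "appropriate tests (t-tests, Mann-Whitney U, Wilcoxon signed-rank", followed by chi-square, Fisher's exact and Pearson correlation. It says that these "were applied based on data characteristics". It does not say which test decides H1 or H2, or whether post-test or change scores are compared.

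The only regression in the document serves another purpose: "Support Vector Regression (SVR) was used to identify clinical and sociodemographic predictors of PSS and PISMI scores". That answers H3, and nothing says that it estimates the arm effect.

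The Randomization section says "Group assignment was carried out using the envelope method to prevent bias". It describes participants drawing envelopes, with no balancing on pre-test scores.

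Study Population and Sample bases the size on stress alone ("Based on the perceived stress scale (PSS) mean scores reported in" a cited study): "the sample was calculated with a 5% type I error, 95% power, and an effect size of 0.924". No effect size is given for stigma, although it has its own hypothesis: "H2: Video-supported orientation training reduces stigmatizing attitudes and beliefs toward psychiatric disorders".

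**The concern.** Of the listed tests, only the two-sample t-test and Mann-Whitney U can compare arms on a scale score, and neither takes a covariate. The signed-rank test (and a paired t-test) compares scores within one arm. Two things follow.

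- **Precision.** A post-test comparison ignores the pre-test score. A change-score comparison uses it with a fixed weight of one, which is worse than ignoring it when the pre-post correlation is below 0.5.
- **Chance imbalance.** With 30 per arm and no balancing on the scales, a visible pre-test gap is quite likely. A post-test comparison carries part of the gap into the estimate, and a change-score comparison over-corrects for it.

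H2 is the more exposed hypothesis. The trial was sized for a large stress effect, and nothing in the protocol shows that the stigma effect is as large.

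**Working it through.** **Inputs from the protocol.** Type I error 5% (sidedness not stated), power 95%, effect size 0.924; minimum 28 per group, 30 per group recruited; both scales at pre-test and post-test.

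**Assumptions.** Pre-post correlation r = 0.3, 0.5 or 0.7; equal SD at both times, set to 1; normal scores; 0.924 read as a post-test effect in SD units. For PISMI, an effect of 0.5 SD is used for illustration.

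**Step 1: the plan's own figure.** For an independent-groups t-test at d = 0.924 and 28 per group, power is 92.4% two-sided and 96.2% one-sided. One-sided, 95% power needs 27 per group by t-test, or 28 by Mann-Whitney (relative efficiency 3/π, power 95.4%). Two-sided needs 32 and 33. So 56 is reproduced as an unadjusted, one-sided, two-group comparison.

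**Step 2: 95% CI half-widths at 30 per arm.**

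- Post-test t-test: t(58) × √(2/30)
- Change-score t-test: t(58) × √[(2/30) × 2(1 − r)]
- ANCOVA: t(57) × √[(2/30)(1 − r²)(1 + 1/56)]; the last factor is the average price of estimating the slope

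| | r = 0.3 | r = 0.5 | r = 0.7 |
|---|---|---|---|
| Post-test | 0.517 | 0.517 | 0.517 |
| Change score | 0.612 | 0.517 | 0.400 |
| ANCOVA | 0.498 | 0.452 | 0.373 |
| Unadjusted post-test n per arm to match ANCOVA | 33 | 39 | 57 |

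Doubling the last row gives 66, 78 and 114 participants. Apart from the one lost degree of freedom, ANCOVA breaks even with the post-test test when (1 − r²)(57/56) = 1, so r = √(1/57) ≈ 0.13. Below that it gains nothing.

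**Step 3: two-sided power at 30 per arm.** Post-test and change-score figures come from the noncentral t, with effect d/√[2(1 − r)] for change scores. ANCOVA figures come from 200,000 simulated trials per setting; with no effect, each single test rejected in 4.9–5.1% of trials.

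| | r = 0.3 | r = 0.5 | r = 0.7 |
|---|---|---|---|
| d = 0.924: post-test | 94.0% | 94.0% | 94.0% |
| d = 0.924: change score | 84.5% | 94.0% | 99.5% |
| d = 0.924: ANCOVA | 95.6% | 98.1% | 99.8% |
| d = 0.5: post-test | 47.8% | 47.8% | 47.8% |
| d = 0.5: change score | 36.3% | 47.8% | 69.1% |
| d = 0.5: ANCOVA | 50.7% | 58.6% | 75.1% |

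One-sided at d = 0.924, post-test power is already 97.1%, against 97.9%, 99.2% and 99.9% for ANCOVA.

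**Step 4: chance pre-test gap.** The SD of the between-arm pre-test difference is √(2/30) = 0.258. A gap of at least 0.3 SD in either direction has probability 2 × [1 − Φ(0.3/0.258)] = 24.5% on a given scale. A gap of 0.3 shifts the post-test estimate by 0.3r = 0.09, 0.15 or 0.21 SD. It shifts the change-score estimate the other way by 0.3(1 − r) = 0.21, 0.15 or 0.09 SD.

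**The case against.** The strongest reply is that nothing here is invalid. An unadjusted comparison of randomised arms keeps its error rate at about 5%, so the point could be called a preference between two valid estimators. That limits its weight, but across the assumed range ANCOVA is more precise than either listed alternative, and the data it needs are already collected.

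A second reply is that the estimator is commonly left to a statistical analysis plan, which may exist unseen. That would answer a complaint about silence. Here the protocol gives an explicit list without an adjusted comparison; if another document adds one, this section still has to agree with it.

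Third, the listed tests could be run on change scores, which do use the pre-test. At a correlation of 0.7 that recovers most of the gain (0.40 against 0.37 SD). This stands, and it means that the figure of 114 participants applies only to a post-test comparison at the top of the assumed range. But the protocol does not say that change scores are compared, and at 0.3 they are clearly worse than the post-test scores alone.

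Three further limits stand in full. The size of the loss rests on a correlation that the protocol does not give. H1 gains little at its planned effect, 1 to 3 points on the one-sided basis that reproduces the sample size. The 0.5 SD effect for PISMI is an assumption.

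**Conclusion.** The concern holds as a loss of precision, not of validity. The listed arm comparisons leave the pre-test scores unused or, as change scores, weighted inefficiently. Against a post-test comparison, ANCOVA narrows the interval by about 4%, 13% or 28% at correlations of 0.3, 0.5 and 0.7 (0.498, 0.452 and 0.373 over 0.517). The two-sided power gain is 2 to 6 points for H1 at the planned effect, and 3 to 27 points at an assumed 0.5 SD effect for H2. Adjustment also removes the shift from a chance pre-test gap, which reaches 0.3 SD in about one trial in four. The correlations and the PISMI effect are assumptions, and below a correlation of about 0.13 there is no gain. The change should be made, but the trial does not fail without it.

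**What to change.** State in the Statistical Analysis section that H1 (PSS-14) and H2 (PISMI) are each judged on one between-arm analysis: post-test score regressed on arm and pre-test score (ANCOVA), reported as an adjusted mean difference with 95% CI, with the sidedness of the test given. Label paired and signed-rank results as descriptive. A rank test between arms may stay as a sensitivity analysis.

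The cost is two sentences, with no new data or participants. Timing is the one complication: Place and Time of the Study puts the trial in the future (2025), while the section on the PSS-14 already reports a reliability coefficient from the current study. If outcome data have been seen, the change cannot restore pre-specification. The adjusted analysis should then be labelled post hoc, given less weight, and reported beside the unadjusted between-arm comparison.

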## **Support Vector Regression-Based Feature Importance Analysis**

Support Vector Regression (SVR) was used to identify clinical and sociodemographic predictors of PSS and PISMI scores. SVR is suitable for small, nonlinear, and high-dimensional datasets common in psychiatry. Feature importance was evaluated using permutation-based analysis, with RMSE increases indicating variable contribution.

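### Read as a rule for identifying predictors, the SVR criterion (an RMSE increase after permutation) does not separate signal from noise

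*Protocol*

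**What the plan says.** The Protocol section Support Vector Regression-Based Feature Importance Analysis gives the purpose: "Support Vector Regression (SVR) was used to identify clinical and sociodemographic predictors of PSS and PISMI scores". It then gives its only reading rule: "Feature importance was evaluated using permutation-based analysis, with RMSE increases indicating variable contribution". No size of increase, reference distribution or evaluation data set is attached to that rule.

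Under Research Questions and Hypotheses, the third question asks "What are the most important variables that determine perceived stress and stigma levels". The list of hypotheses opens with "Accordingly, the following hypotheses were tested", and H3 begins "Perceived stress and stigma levels are influenced by various factors". The study title also names the method: "Feature Importance Analysis Using Support Vector Regression". The section Statistical Analysis lists general tests, Pearson correlation among them, but assigns none of them to H3.

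**The concern.** Permutation importance measures how much the prediction error grows when one variable is scrambled. It can be positive for a variable that has nothing to do with the outcome. On the data used for fitting, the model has adapted to chance patterns in every column, so scrambling almost any column worsens the fit. On held-out data, a model fitted to noise predicts nothing before or after scrambling, so the error moves up or down by chance.

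A section that sets out to find predictors, and takes an increase as the sign of one, will therefore usually return a list even when no variable matters. H3 claims only that some factors matter, so almost any non-empty list could be taken as support for it. The third research question and part of the study title rest on the same output.

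**Working it through.** The plan gives no figure for the SVR analysis, so there is none to reproduce. Its sample size calculation concerns the two-group comparison of PSS means.

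**Inputs from the Protocol.** 60 participants, 30 per group (Study Population and Sample); two outcomes, PSS and PISMI; the criterion quoted above.

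**Assumed, because the Protocol does not give them.** Varied: RBF kernel with C = 0.1, 1 and 10, and linear kernel with C = 1; 3, 5, 10 or 15 predictors (H3 names three groups of factors, so 3 is a floor). Held fixed: epsilon 0.1, gamma = 1/p, half the predictors binary, 5 folds, 10 permutations per variable.

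**Formula.** RMSE = sqrt[ Σ(yᵢ − ŷᵢ)² / n ]. The importance of variable j is the mean RMSE after permuting column j minus the RMSE with the column intact. The rule examined is: importance above zero means contributor.

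**Step 1: no true relationship, n = 60, 200 data sets per setting.** On the fitted data, 100% of noise variables (RBF) or 79-82% (linear) show an increase. On held-out data, for 3 / 5 / 10 / 15 predictors:

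| Model | Share of noise variables with an increase | Data sets with at least one increase, one outcome |
|---|---|---|
| RBF, C=0.1 | 0.448 / 0.460 / 0.435 / 0.426 | 0.755 / 0.915 / 0.985 / 1.000 |
| RBF, C=1 | 0.443 / 0.501 / 0.451 / 0.433 | 0.730 / 0.895 / 0.975 / 1.000 |
| RBF, C=10 | 0.468 / 0.517 / 0.470 / 0.437 | 0.685 / 0.875 / 0.970 / 1.000 |
| Linear, C=1 | 0.398 / 0.399 / 0.410 / 0.428 | 0.770 / 0.910 / 1.000 / 1.000 |

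For example, RBF with C=1 and 10 predictors gives 10 × 0.451 ≈ 4.5 false contributors per data set. The Monte Carlo standard error of the 0.730 entry is sqrt(0.73 × 0.27 / 200) ≈ 0.03. With two outcomes, the chance of at least one increase cannot be lower than with one.

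A separately programmed simulation (RBF, C=1, 100 data sets, 20 permutations per variable) gave 100% on fitted data. On held-out data it gave 43%, 44% and 46% for 5, 10 and 15 predictors, with at least one increase in 86%, 98% and 100% of data sets. A further run over both kernels gave 38-48% held-out, with at least one in 67-100%.

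**Step 2: is the small sample the cause?** Held-out share at n=60 against n=300 (C=1; 60 data sets at n=300):
- 3 predictors: RBF 0.472 against 0.483, linear 0.398 against 0.400
- 10 predictors: RBF 0.478 against 0.462, linear 0.409 against 0.413

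The share does not fall, so the cause on held-out data is the zero cut-off. A larger sample does shrink spurious increases on fitted data (RBF, 3 predictors: 0.102 against 0.043 outcome SD).

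**Step 3: does the size of the increase carry information?** One true predictor, n=60, 300 data sets per setting, held-out data. Proportion in which it ranks first, for 3 / 5 / 10 / 15 predictors:
- r=0.5: RBF (C=1) 0.937 / 0.937 / 0.920 / 0.950; linear 0.980 / 0.983 / 0.947 / 0.903
- r=0.3: RBF (C=1) 0.673 / 0.573 / 0.467 / 0.503; linear 0.820 / 0.683 / 0.590 / 0.460

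Chance alone gives 1/p = 0.33 / 0.20 / 0.10 / 0.07. The ranking is therefore informative, less reliably so for the weaker predictor. Even so, with one true predictor among 10, about 4 of the 9 noise variables still show a held-out increase (RBF 4.2-4.3, linear 3.8).

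**Step 4: a reference that works.** RBF, C=1, twice-repeated 5-fold, 5 permutations per variable, 99 outcome permutations, 100 data sets. Chance of at least one false contributor for 3 / 5 / 10 predictors:
- increase above zero: 0.67 / 0.92 / 0.97
- above the 95th percentile of the maximum importance under permuted outcomes: 0.03 / 0.05 / 0.04
- the same, and the SVR must also beat a mean-only model: 0.01 / 0.05 / 0.03

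The last two rows differ by no more than the Monte Carlo error, sqrt(0.05 × 0.95 / 100) ≈ 0.02. With 3 and 10 predictors, the SVR beats mean-only in 0.69 and 0.68 of data sets at r=0.5, and in 0.36 and 0.29 at r=0.3. As a compulsory condition it would block interpretation in 31-32% and 64-71% of data sets that contain a real predictor.

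**The case against.** **The sentence may only define the metric.** It can be read as saying that a larger loss of accuracy means a larger contribution. It does not say that any increase suffices, and it names no cut-off at zero. The title and the third research question fit a ranking. This stands as a fair reading, and it is why the point is conditional. But the section's stated purpose is to find predictors and no other criterion is given. A ranking alone does not close the gap, since some variable ranks first even when none matters.

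**Thresholds, folds and tuning belong in an SAP.** Agreed: their absence is no finding here, and an unseen SAP could add a reference. The point concerns the reading rule the Protocol does state.

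**A reader might infer that the SVR can never bear on H3, or that H3 is to be declared supported by any positive importance.** The documents support neither. No rule ties RMSE increases to H3, the tests under Statistical Analysis could address it separately, and Step 3 shows that the size of an increase carries information.

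**The rates rest on assumptions.** True. Epsilon and gamma were not varied, the fitted-data figures apply only if importance is scored on the fitting data, and the n=300 comparison is small. The exact percentages are indicative; the direction held in every setting tried.

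**Conclusion.** The point holds in a limited form. If the stated criterion is used to decide which variables contribute, it fails: under a complete null at n=60, about 80-100% of noise variables pass on fitted data and about 40-50% on held-out data. At least one passes on held-out data in about 70% of data sets with 3 predictors, rising to nearly all with 10 or more. Only the bare presence of an increase is uninformative; its size is not.

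The conclusion rests on assumed kernels, C values and predictor counts, and on the sentence being read as a decision rule, which the wording permits but does not compel. The randomised comparison is untouched: H1, H2 and the tests under Statistical Analysis do not depend on it. The correction is worth making because it is cheap and concerns an aim named in the title.

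**What to change.** Choose one of two routes and state it in the SVR section.

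1. **Identification.** Compute permutation importance on held-out folds, for example repeated 5-fold cross-validation, with any tuning done inside the training folds. Call a variable a contributor only if its RMSE increase exceeds a reference obtained by permuting the outcome and refitting. One suitable choice is the 95th percentile of the maximum importance over all predictors.
2. **Description.** Present the importances as an exploratory ranking, say that an increase does not by itself show contribution, and do not present the result as a test of H3.

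Under either route, report held-out RMSE beside that of a mean-only model as context, not as a condition for interpretation. In the null simulations the SVR averaged 1.01-1.29 outcome SD against 1.00-1.01 for mean-only in all 16 settings, so the comparison tells the reader something.

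**Cost.** Route 1 needs some computing time and a paragraph of text, and it declares fewer variables. With the maximum threshold plus the mean-only condition (RBF, C=1), a predictor with r=0.5 was declared in 60% of data sets with 3 predictors and 52% with 10; with r=0.3, in 20% and 10%. Dropping the mean-only condition, as advised here, can only leave these rates equal or raise them, but weak predictors should still be expected to be mostly missed at n=60. Route 2 costs only the wording and the RMSE report.
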